## **Proton Beam Radiotherapy**

Proton beam radiotherapy has physical properties that target the actual tumor mass and spare large portions of nearby normal tissues. Phase I and II trials demonstrated the safety of this treatment modality in decompensated patients with cirrhosis with HCC. Few trials in Southeast Asia and the United States demonstrated that proton beam could be an effective treatment that may improve survival and control tumor progression. Tokuyue et al. treated 79 patients who had HCC with proton beam radiotherapy (12). A median total dose of 72 Cobalt gray equivalents in 16 fractions was delivered. At 5 years, local tumor control and survival rates were 89% and 27% respectively. Kawashima et al. used the same fractionation scheme in 30 patients with HCC with an indocyanine green retention rate at 15 minutes. Complete disappearance of tumors occurred in 24 patients (80%). The 2-year local regression-free rate in that study was 96%, and the 1-year and 3-year survival rates were 77% and 62% respectively (13). Eight patients developed hepatic insufficiency, which presented as ascites, elevated transaminase levels, and/or asterixis from 1 to 4 months after therapy (13). Bush et al., in a phase II trial where 34 patients with HCC completed 15 sessions of total 63 cobalt Gray equivalents, 75% local tumor control rate and overall survival rate of 55%. Six patients underwent liver transplantation 6 to 18 months after proton therapy. In 2 patients, there was no evidence of tumor pathology, demonstrating that proton therapy can eradicate HCC (14). A complete pathologic response was also observed by Merle et al (15). Risks involved in proton treatment include internal bleeding, radiation hepatitis (elevation in liver enzymes), worsening liver function (elevation in

bilirubin and INR) and perforation of the surrounding solid organ such as small bowel and stomach.

Proton beam radiotherapy has been associated with some of the best outcomes in HCC patients; however, further studies are needed to compare proton to other treatments.

In this randomized trial we wish to compare head-to-head the efficacy of proton beam radiotherapy versus TACE in treating patients with unresectable HCC.

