## ***Primary Endpoint***

The primary end point of the study is to measure ***overall survival*** defined as the time from randomization until death. In order to control for non-cancer death related factors that may compound the survival rate, a competing risk analysis rather than Kaplan-Meier will be used to compare the survival between the two groups.

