## **2. Downstaging**

This endpoint will be applied to subjects in whom their tumor burden exceed Milan criteria but meet San Francisco criteria (Appendix 1). The direct measurement of the longest diameter of the viable tumor will be compared pre-and-post treatment. Usually, patients with San Francisco criteria will not be qualified for MELD score exception upgrade on UNOS waiting list unless their tumor burden is down-staged to Milan criteria using one of the locoregional treatments. Measuring this endpoint will help in comparing the efficacy of proton versus TACE in downstaging tumor in patients who meet San Francisco criteria.

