## ***Follow Up***

Patients with HCC usually require either CT scan or MRI of the abdomen to be performed routinely every three months to monitor tumor progression. Patients undergoing any locoregional treatment usually require a CT scan or MRI of the abdomen to be performed 4-6 weeks after the treatment and then every three months. Follow up imaging will be the same modality used at baseline (CT or MRI). Patients are usually evaluated in the liver clinic 4 weeks after treatment and then every three months. Subjects receiving proton therapy will also be followed in radiation medicine clinic by their treating radiation oncologist every 3 months for the first year then every 6 months. Participants in this study will be followed according to this protocol. No radiological testing will be ordered for the purpose of the study as the recommended assessments follow the current standard of care. Patients will be followed for research purposes until death or transplant, or until which time the study investigators determine the study is complete.

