## **Data and Statistics**

Data will be evaluated according to intent to treat analysis. One- and two-year survival will be compared between two groups using competing risk analysis. This analysis will provide an estimate of HCC-related death in the presence of alternate yet plausible outcomes such as death from liver failure or liver transplantation. It is also a better technique in illustrating differential rates of competing outcomes in patients waiting for liver transplantation. This analysis will limit the effects of confounding factors such as death from liver disease. Secondary end points will be compared using Student's *t*-test for quantitative data and chi-squared ( $\chi^2$ ) test or Fisher's exact test for qualitative data. Demographics and standard of care laboratory data between groups will be compared. Logistic regression will be used to determine independent factors affecting survival.

The study is designed and powered to show at least 15% difference in mortality between two groups. Group size is calculated by assuming that patients in the TACE group will have at least 15% improvement in 2-year survival compared to the proton beam group. With 110 patients in each group the study has 80% power to detect a 15% difference in the mortality between two groups. We are not expecting any significant drop out because both treatments are considered crucial for patients' survival; and also based on our experience in treating these patients for many years at LLUMC. The level of significance is 0.05 (2-sided) for all statistical tests. The Statistical Package for the Social Sciences (SPSS 16.0 for window; SPSS, Inc., Chicago, Illinois) was used for all statistical analyses.

We will conduct an interim analysis after randomizing 40 patients in each group. This analysis will determine if there is any early significant difference in survival between two groups. The interim report will be submitted to the Institutional Review Board.

Data will be collected anonymously and subjects will be identified using a numerical code. The code will be stored at the PI and Co-PI office. The study database will be maintained and stored in the department of radiation medicine. Only PI, CO-PI and research coordinators will have access to the data.

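### Logistic regression for factors affecting survival ignores follow-up time and transplant, so factors tied to transplant access can look prognostic when they are not, or have their effect diluted or exaggerated

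*Combined protocol and SAP*

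**What the plan says.** All references are to the combined protocol and SAP.

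- **Data and Statistics**, on prognostic factors: "Logistic regression will be used to determine independent factors affecting survival". It gives no time point, no list of factors, and no rule for patients who are transplanted or incompletely followed.
- **Primary Endpoint**: overall survival is "defined as the time from randomization until death".
- **Follow Up**: "Patients will be followed for research purposes until death or transplant, or until which time the study investigators determine the study is complete".
- On comparing the arms (**Data and Statistics**): "One- and two-year survival will be compared between two groups using competing risk analysis". The reason given is that HCC death occurs alongside "alternate yet plausible outcomes such as death from liver failure or liver transplantation". This method is not extended to the factor analysis.
- **Downstaging**: patients beyond Milan but within San Francisco criteria usually "will not be qualified for MELD score exception upgrade on UNOS waiting list unless their tumor burden is down-staged to Milan criteria". Appendix 5 adds that organ priority goes to the highest MELD scores.

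**The concern.** Logistic regression needs one known outcome per patient at one common time. The plan does not collect that. Death after transplant is not observed, and follow-up otherwise ends on a date the investigators choose. The analyst must therefore code a transplanted patient as alive or leave the patient out, and the plan does not say which.

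This would matter little if transplant were unrelated to the factors under study. But the protocol itself says that tumour burden and MELD affect access to transplant, and both are obvious candidates for a prognostic model. A factor that only moves patients to transplant changes how many can be seen to die, and the model reads that as an effect on death. Conversely, a factor that raises both death and transplant can have its effect hidden.

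At stake is whether the trial's list of prognostic factors can be trusted. This is also the only multivariable survival model in the plan.

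**Working it through.** The plan gives no figure for this analysis. Its 110 per group belongs to the arm comparison and is used here only for the total of 220.

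**Inputs**
- From the documents: 220 patients; two-sided 0.05; a 2-year horizon; 63% two-year survival, the TACE result of the cited 2002 randomized trial.
- Assumed: a yes/no factor in 110 of 220; constant death and transplant rates; the transplant contrasts below. A contrast of 40% v 10% means the rates that would transplant 40% and 10% by 2 years if nobody died. The only transplant frequency in the documents is in the cited phase II proton trial: "Six patients underwent liver transplantation 6 to 18 months after proton therapy", that is 6/34, about 18%.

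**Formulas, status fixed at 2 years**
- Death rate λ = −ln(0.63)/2 = 0.2310 per year. Transplant rate τ = −ln(1 − p)/2.
- Dead before transplant: D = λ/(λ+τ) × [1 − exp(−2(λ+τ))].
- Alive and not transplanted: A = exp(−2(λ+τ)).
- Odds ratio (OR) with transplanted coded alive: ratio of D/(1 − D). With transplanted dropped: ratio of D/A.
- Time-to-event comparator: log hazard ratio (HR), with SE = √(1/deaths₁ + 1/deaths₀).

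**A factor with no effect on death, transplant 40% v 10%**
- τ = 0.2554 and 0.0527.
- With the factor: D = 0.2310/0.4864 × (1 − 0.63×0.60) = 0.4749 × 0.622 = 0.295.
- Without it: D = 0.2310/0.2837 × (1 − 0.63×0.90) = 0.8143 × 0.433 = 0.353.
- Coded alive: OR = (0.2954/0.7046)/(0.3526/0.6474) = 0.77. SE = √(1/32.5 + 1/77.5 + 1/38.8 + 1/71.2) = 0.289. z = 0.261/0.289 = 0.90, so it is significant in about 15% of trials.
- Dropped: OR = (0.2954/0.378)/(0.3526/0.567) = 1.26. The false signal changes direction.
- Time-to-event: the log HR is 0, so 5%.

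**A true HR of 1.6, transplant 40% v 15%**
- Death rate with the factor: 1.6 × 0.2310 = 0.3696. D = 0.422 with it and 0.344 without.
- Coded alive: OR = 1.39, z = 0.332/0.2785 = 1.19, power about 22%.
- Time-to-event: z = 0.470/√(1/46.4 + 1/37.8) = 0.470/0.219 = 2.15, power about 57%.
- With no transplants the OR would be (0.5225/0.4775)/(0.37/0.63) = 1.86.

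| Transplant, with v without factor | True HR | Coded alive: OR, significant | Dropped: OR, significant | Time-to-event significant |
|---|---|---|---|---|
| 30% v 10% | 1.0 | 0.85, 9% | 1.15, 7–8% | 5% |
| 40% v 10% | 1.0 | 0.77, 15% | 1.26, 11% | 5% |
| 40% v 15% | 1.6 | 1.39, 22% | 2.29, 76% | 57% |
| 15% v 40% | 1.6 | 2.27, 82% | 1.54, 28% | 56% |
| 20% v 20% | 1.6 | 1.80, 56% | 1.87, 56% | 59% |

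Simulation of the same 2-year scenarios agrees to within 1 to 3 points. It gives 21% v 56% for the third row and up to 58% v 61% for the last.

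**Status at study close** (simulated; accrual of 3 to 5 years and at least 2 years of follow-up, both assumed; coded alive)
- No effect on death: falsely significant in 18–38% at 27–30% v 9–10% transplanted, and in 46–66% at 40% v 10%. Log-rank stays at about 5%.
- HR 1.6 at 40% v 15%: power 5–8%, against about 70%.
- Transplant unrelated to the factor: no false signal; power about 60–62%, against 73–77%.

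**Sensitivity at the documented level.** Hold overall transplant near 18% by 2 years and let the factor multiply the transplant rate by 3, 5 or 10. A factor with no effect on death is then falsely significant in 8.7%, 12.4% or 17.4% of trials (coded alive). At 8% v 21% actually transplanted it is about 6.5%.

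**The case against.** The natural reading of the sentence is status at one or two years, since those are the horizons named for survival. On that reading the figures are moderate: 9–15% false positives, and a real factor weakened but not lost. This stands, and the 2-year figures should be read first. The study-close figures show what happens if the missing time point is filled in the other way.

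The transplant contrasts and accrual are not in the documents. That also stands: the size is conditional, and with little transplant, or transplant unrelated to the factor, the harm is small.

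Coding transplanted patients as alive at 2 years does estimate something definite, the cumulative incidence of death before transplant. True, but it is not an effect on survival, and the plan neither names it nor adopts the coding.

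Three stronger readings are tempting and not supported.

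- A reader might infer that transplant-related factors will look prognostic and real ones will disappear. Near-total loss needs heavy, unequal transplant and status at study close.
- A reader might infer that tumour burden would be masked. If larger burden raises death and lowers access, coding transplanted patients alive exaggerates it (fourth row of the table); dropping them dilutes it. Masking under the coded-alive rule needs a factor that raises both death and access. MELD is the documented candidate, and its range is limited by excluding scores above 25 and Child class C.
- A reader might infer that an adjusted treatment effect is distorted. The plan lists no covariates and does not say that arm enters this model.

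**Conclusion.** The point holds and should be corrected. The stated model does not fit an endpoint defined as a time when observation stops at transplant, and nothing else in the plan repairs it. Expecting little dropout does not help, because transplant is not dropout.

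At the plan's 2-year horizon, with transplanted patients coded alive, the false-positive rate for a factor that affects only transplant is roughly 9–15% instead of 5%. Power for a true HR of 1.6 that also raises transplant is roughly 21% instead of 56%. At study close the errors are several times larger. With transplant unrelated to the factor there is no false signal and only some loss of power.

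These sizes rest on 63% two-year survival borrowed from a cited trial, constant rates, a 50/50 factor, and assumed transplant contrasts and accrual. The existence of the problem does not rest on them. This is a secondary prognostic analysis; the randomized comparison has its own method and is not touched by this sentence.

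**What to change.** Replace the logistic regression sentence in Data and Statistics with:

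> Factors affecting survival will be examined with a Cox model of time from randomization to death, with treatment arm and prespecified baseline factors (for example Child class, MELD, within/beyond Milan, AFP), censoring patients when last known alive and at transplant. Results are cause-specific hazards of death before transplant. A Fine-Gray model treating transplant as a competing event will be a companion analysis.

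The third sentence is needed. Censoring at transplant does not give the effect on overall survival unless transplant is unrelated to prognosis, which the protocol gives reason to doubt. If the team wants effects on overall survival, the alternative is to keep recording vital status after transplant, which means changing Follow Up and collecting more data. The factors listed are examples; the team should fix its own list before looking at outcomes.

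Cost: one short replacement and no new data, since the dates of death, transplant and last contact are already needed for the competing risk analysis. It adds a proportional-hazards check, slightly more analysis work, and confirmation that the named software fits both models.

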## **Transarterial Chemoembolization (TACE)**

Multiple studies have shown contradictory results regarding the efficacy of TACE in improving survival compared to other treatments. The majority of these studies are retrospective studies or used a small sample of patients. These contradictory results have been attributed to the difference in endpoints of these studies and the multiple variables such as tumor size and liver function that usually impact and confound the outcome.

In one large study involving several institutions in Italy, chemoembolization did not improve survival compared to supportive care only. Patients who did not undergo TACE lived as long as patients who received TACE, even though the tumors were more likely to shrink in size in patients who were treated (8). Llovet et al. used TACE as a palliative treatment in a prospective, randomized controlled trial published in 2002 on 112 patients with intermediate stage HCC not felt to be candidates for other therapies. The patients randomized to TACE versus supportive care only. A significant increase in survival for the chemoembolization group was observed when compared with control (82% and 63%, 1-and 2-year survival, respectively, compared with 63% and 27%) (9). A study in Japan has shown that TACE can downstage liver cancer (10). Downstaging created the option for transplant in some of these patients. Otherwise, these patients had tumors that were not operable (eligible for operation) or not qualified for liver transplantation because of the initial large size of their tumors (10). More importantly, this study showed an improvement in survival in patients whose tumors became considerably smaller. In the U.S., trials are underway to see whether doing TACE before liver transplantation increases patient survival as compared to liver transplantation without TACE. Risk and common side effects of TACE include: bleeding, infection, worsening liver function, perforation of the common bile duct, veins or arteries, abdominal pain, nausea, vomiting, and fever.

It is reasonable to conclude that TACE is a procedure with acceptable side effects and a controversial small advantage in improving survival, especially in patients with small tumor and for patients waiting for liver transplantation. TACE can be used only in patients with relatively preserved liver function. The reason for this is that these procedures, as mentioned previously, can lead to liver failure in individuals with poor liver function.

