## ***Methods***

Patients meeting the inclusion and exclusion criteria will be randomized (1:1) by an individual who is not a study investigator using the random number method. Subjects will be registered and randomized by contacting [name] ([name], [[contact]](mailto:[contact])). Subjects will be randomly assigned to one of two groups:

Group 1: patients will receive one or more sessions of TACE (Appendix 3).

Group 2: patients will receive 15 consecutive sessions of proton beam radiation (Appendix 4).

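### The 80% power for 110 per group makes no allowance for transplant, where research follow-up ends; at the cited 6 of 34 it would be about 75-77%, given equal rates in both groups and a baseline where 80% would otherwise hold

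*Combined protocol and SAP*

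**What the plan says.** Data and Statistics gives the size and the claim: "With 110 patients in each group the study has 80% power to detect a 15% difference in the mortality between two groups". The time point and direction come from the sentence before it, which sizes the groups by "assuming that patients in the TACE group will have at least 15% improvement in 2-year survival compared to the proton beam group". No 2-year survival rate is given for either group. Testing is two-sided at 0.05, and Methods specifies 1:1 allocation.

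On loss, the same section says: "We are not expecting any significant drop out because both treatments are considered crucial". It adds the centre's own experience as a second reason and states no inflation of the group size.

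Three other places bear on transplant:

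- Follow Up: "Patients will be followed for research purposes until death or transplant", or until the investigators judge the study complete.
- Data and Statistics, on the competing risk analysis, lists liver transplantation and death from liver failure as alternate outcomes to HCC-related death.
- Proton Beam Radiotherapy, on the cited phase II series of 34 patients: "Six patients underwent liver transplantation 6 to 18 months after proton therapy".

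Primary Endpoint defines overall survival as time from randomization to death and does not mention transplant.

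**The concern.** A patient transplanted before 2 years leaves research follow-up at that moment, so any later death within the 2 years is not observed. The design expects transplants. Recruitment is partly from the Transplantation Institute's liver clinics, the Introduction gives bridging and downstaging to transplant as goals of locoregional treatment, and downstaging is a secondary endpoint. The analysis text foresees transplant, but the sample-size text does not.

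Two things follow. If transplant is a competing event, some deaths that would have occurred by 2 years are pre-empted in both groups, and the observable difference falls below the 15 points the trial was sized on. If transplant is treated as censoring, the difference is kept but its variance rises. Either way the power is lower than the figure computed without transplant, provided the transplant rate is similar in the two groups. A non-significant result would then be read against a claimed 80% that the plan had not secured.

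**Working it through.** **Inputs from the documents.** n = 110 per group; two-sided alpha 0.05; a 15-point difference in 2-year mortality (all Data and Statistics); 6 transplants among 34 patients, 6/34 = 17.6%, at 6 to 18 months (Proton Beam Radiotherapy).

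**Assumptions, not in the documents.** The 2-year survival rates; exponential death times; transplant timing independent of death; the same transplant rate in both groups unless stated; all deaths counted as events.

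**Step 1: the plan's own figure.** Two-proportion power with pooled null variance:

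power = Φ[(Δ − 1.96·SE0)/SE1], where SE0 = √(2·p̄(1−p̄)/n) and SE1 = √((p1(1−p1)+p2(1−p2))/n).

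The 80% cannot be reproduced directly because no baseline is stated. Working backwards, it is met exactly at survival of 87.6% v 72.6% or 27.4% v 12.4%. I use the rounded pair 88% v 73%, that is, mortality 0.12 v 0.27: SE0 = 0.0534, SE1 = 0.0525, power = Φ[(0.15 − 1.96 × 0.0534)/0.0525] = 80.6%.

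**Step 2: transplant at a constant rate.** Death hazards per year: −ln(0.88)/2 = 0.0639 and −ln(0.73)/2 = 0.1574. Transplant hazard: g = −ln(1 − 6/34)/1.5 = 0.129. Carried on to 24 months, this implies 1 − exp(−2 × 0.129) = about 23% transplanted by 2 years if no one died first.

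Competing event: the 2-year incidence of death is h/(h+g) × (1 − exp(−2(h+g))), giving 0.106 v 0.239. The difference is 13.3 points and power is 74.8%.

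Censored at transplant: Greenwood variance of 2-year survival is S²·[h/(h+g)]·(exp(2(h+g)) − 1)/n, giving 0.00110 and 0.00206. Power = Φ(0.15/√0.00316 − 1.96) = 76.1%.

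**Step 3: transplant at the reported times.** Let 6/34 of each group have a transplant time spread evenly over 6-18 months, with none afterwards. The average probability of dying before such a time is 0.062 v 0.145. Incidence of death by 2 years: (28/34) × 0.12 + (6/34) × 0.062 = 0.110, and (28/34) × 0.27 + (6/34) × 0.145 = 0.248. The difference is 13.8 points and power is 76.6%. A simulation at 87.6% v 72.6% with the same timing (6,000 runs) gives 77% both for a log-rank test censored at transplant and for a competing-risk test, against 81% without transplant.

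**Step 4: sensitivity at 88% v 73%, n = 110.**

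| Transplant assumption | Difference as competing event (points) | Power, competing event | Power, censored |
|---|---|---|---|
| None | 15.0 | 80.6% | 80.6% |
| 6/34, evenly at 6-18 months | 13.8 | 76.6% | about 77% (simulated, 87.6% v 72.6%) |
| 6/34 by 18 months, constant rate | 13.3 | 74.8% | 76.1% |
| 30% by 2 years (assumed) | 12.8 | 72.7% | 73.9% |
| 40% by 2 years (assumed) | 12.0 | 69.3% | 70.2% |

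**Step 5: unequal rates.** With the Step 2 hazard in one group only, as a competing event: if only the group with worse survival is transplanted, mortality is 0.120 v 0.239 and power 64%. If only the group with better survival is transplanted, it is 0.106 v 0.270 and power 88%.

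**Step 6: other baselines.** The only 2-year TACE survival in the documents is the 63% of the trial cited under Transarterial Chemoembolization ("82% and 63%, 1-and 2-year survival, respectively, compared with 63% and 27"), which is not declared as the design rate. At 63% v 48% power is 61% before any transplant, and 54% with the Step 2 hazard as a competing event. At 92% v 77% power with transplant is still 82% (Step 2 timing) to 84% (Step 3 timing).

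**The case against.** The strongest reply is that transplant is not drop-out in this plan. The quoted sentence gives the importance of treatment as its reason, which reads as a statement about withdrawal, and the same section handles transplant separately as an alternate outcome. This stands: the sentence may be true as written, and nothing requires its deletion. It does not rescue the 80%, because naming transplant in the analysis does not put it into the power.

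A reader might infer that transplanted patients are lost outright. That would leave 110 × 28/34 = 90.6 per group and about 72% power. The documents do not support this, since these patients contribute follow-up until transplant.

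A reader might also take 69% as the consequence of the cited series. It is not: it needs an assumed 40% transplant rate, which appears nowhere in the documents.

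Nor can one say that 80% is out of reach at any survival rates. At 92% v 77% it is exceeded even with transplant. At 27.4% v 12.4%, the other back-solved pair, simulation with transplants at 6-18 months gives 87% for a log-rank test censored at transplant and 85% for a competing-risk test (both 88% without transplant), although a simple 2-year comparison falls from 80% to 76%.

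Two further objections stand as limits. The missing baseline moves power more than transplant does. And 6/34 is one small proton-only series with no TACE counterpart, so equal rates are an assumption, and without it the direction of the effect is not fixed.

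**Conclusion.** The point holds at moderate size. The stated power omits a loss of information that the follow-up rule builds in and the analysis text acknowledges. At the only transplant rate in the documents, power falls from about 80% to about 75-77%, with an observable difference of about 13.3-13.8 points rather than 15. The spread reflects transplant timing and whether transplant is a competing event or censoring.

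This rests on a back-solved baseline, equal transplant rates, independence of transplant and death, and all deaths counting as events. The 69-74% at transplant rates of 30-40% is sensitivity only, and the 64-88% for one-sided transplant shows how much the equal-rate assumption carries. The shortfall does not make the trial uninformative. It means that 80% should not stand as the figure for the planned analysis without the rates behind it.

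**What to change.** In Data and Statistics:

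1. Limit the drop-out sentence to withdrawal and loss to follow-up, and say that transplant is dealt with separately.
2. State the assumed 2-year survival and the expected 2-year transplant proportion in each group, with their sources.
3. Restate the power of 110 per group for the planned competing-risk analysis with transplant included. On the rates used above this is about 75-77% at the cited transplant rate, with 30%, 40% and unequal rates shown as sensitivity. If the sponsor's own survival rates differ from 88% v 73%, the figure must be recomputed from them.

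Reconcile Primary Endpoint, Follow Up, and Data and Statistics on whether a death after transplant counts. The endpoint definition includes any death, the follow-up rule stops before it could be seen, and the analysis text treats transplant as an alternate outcome. The power statement should match whichever reading is adopted.

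The cost is protocol wording and a short recalculation. Enrolment need not change. The one drawback is that the stated power is likely to be less favourable.

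### The interim survival comparison has no boundary, no adjusted final level and no stated consequence; tested at 0.05 both times, the overall type I error is about 9%.

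*Combined protocol and SAP*

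**What the plan says.** All the relevant text is in Data and Statistics.

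- Timing: "We will conduct an interim analysis after randomizing 40 patients in each group. This analysis will determine if there is any early significant difference". The trigger is a count of patients randomized, with no required number of deaths or length of follow-up.
- Purpose, in full: "This analysis will determine if there is any early significant difference in survival between two groups". The Primary Endpoint section makes overall survival the primary endpoint, so this is an early test of the main comparison.
- Level: "The level of significance is 0.05 (2-sided) for all statistical tests". No separate level is given for the interim or the final test, so this sentence covers both.
- Follow-on: "The interim report will be submitted to the Institutional Review Board".
- Final size: "With 110 patients in each group the study has 80% power to detect a 15% difference in the mortality between two groups".

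The document gives no stopping or claiming boundary, spending function, adjusted final level or monitoring committee. It does not say what happens if the interim result is significant, and it does not say that the look is for information only.

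**The concern.** Testing the same hypothesis twice at 0.05, with either result allowed to count, gives a true null more than a 5% chance of being rejected. The plan's stated significance level would then not be the error rate of its primary comparison.

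The wording points towards a look that counts, because its purpose is to establish significance, but no rule follows from it. Sending a report to the review board is a reporting step, not a decision rule. The Follow Up section also leaves the investigators to decide when the study is complete, and Data and Statistics gives the principal investigators access to the data. That does not suggest they would stop early on a favourable result; it means nothing in the plan governs the matter. Once interim results have been seen, a rule written afterwards carries little weight.

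**Working it through.** **The plan's own figure.** The plan states no overall type I error, so there is none to reproduce. Its 80% power with 110 per group cannot be confirmed, because no baseline 2-year survival is given. That is a separate matter and does not enter the calculation below.

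**Inputs from Data and Statistics and Methods.** Two-sided 0.05 at each test (critical value 1.96); interim at 40 + 40 = 80 patients; final at 110 + 110 = 220; 1:1 allocation.

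**Formula.** Under no difference, the interim and final statistics Z1 and Z2 are approximately bivariate normal with correlation √t, where t is the fraction of the final information available at the look. Then

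overall error = 1 − P(|Z1| < 1.96 and |Z2| < 1.96).

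| t | overall error |
|---|---|
| 0.05 | 9.6% |
| 0.09 | 9.5% |
| 0.20 | 9.2% |
| 0.30 | 8.9% |
| 80/220 = 0.364 | 8.7% |

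As t approaches 0 the limit is 1 − 0.95² = 9.75%.

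**Which t applies.** For survival, information follows deaths rather than patients, and at the look most patients have had little follow-up. The plan gives neither accrual rate nor baseline survival, so these are assumptions: 1 to 8 patients a month, 2-year survival S of 45% to 70%, exponential survival with monthly hazard λ = −ln(S)/24, and a final analysis 24 months after the last randomization. Expected deaths are the sum over patients of 1 − exp(−λ × months since entry).

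Example with S = 55%, counting all deaths:

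| patients a month | deaths at look / at final | t | overall error |
|---|---|---|---|
| 1 | 45 / 198 | 0.23 | 9.1% |
| 2 | 29 / 178 | 0.16 | 9.3% |
| 4 | 17 / 154 | 0.11 | 9.5% |
| 8 | 9 / 132 | 0.07 | 9.6% |

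Over the whole assumed range, counting all deaths gives t = 0.06 to 0.25 and an error of 9.1% to 9.6%. Counting only deaths within 24 months of randomization gives t = 0.09 to 0.31 and 8.9% to 9.5%.

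**Simulation.** With so few deaths at the look the normal approximation is rough. Simulating 20,000 null trials per accrual rate (S = 55%, log-rank test on all deaths standing in for the competing-risk test) gave rejection at either look in 9.3%, 9.5%, 9.3% and 9.6% of trials at 1, 2, 4 and 8 patients a month, with a Monte Carlo standard error of 0.2 percentage points.

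**Check of the remedy.** With an interim level of 0.001 and a final level of 0.049, the overall error cannot exceed 0.001 + 0.049 = 0.05 at any t; the same formula gives 4.94% to 4.99% for t from 0.364 down to 0.05. The final level that gives exactly 5% is 0.0491 to 0.0496 over that range. Leaving the final test at 0.05 gives 5.0% to 5.1%.

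**Power.** A test with 80% power at 0.05 has a standardized effect of 1.960 + 0.842 = 2.802. At a final level of 0.049 the critical value is 1.969, so power is Φ(2.802 − 1.969) = 79.8%; at 0.0496 it is 79.9%.

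**The case against.** The strongest reply is that the harm is conditional. The plan never says a significant look would stop the trial or be claimed as a result. If the review board simply receives a report and the final test is done regardless, the final test keeps its 5%. That is correct, and it is why the 9% is stated as conditional. It does not clear the plan, because a look whose declared purpose is to find a significant difference, under a level that covers every test, cannot be read as descriptive without a sentence saying so.

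Other points have partial force:

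- At 4 to 8 patients a month, with 55% survival, the look would rest on only 9 to 17 deaths, so few people might rely on it. A test at 0.05 still produces false positives at about that rate however little information it has.
- One patient a month implies 220 months of enrolment, which is implausible. Dropping that case limits t to about 0.18 (all deaths) or 0.27 (deaths within 24 months) and narrows the error to about 9.0% to 9.6%. The conclusion does not move.
- The competing-risk analysis is described as estimating HCC-related death, with liver-failure death and transplantation as competing outcomes, so it is unsettled which deaths count. This matters for any boundary computed from the fraction of deaths; it does not affect a fixed 0.001 / 0.049 split.
- The 80% power is taken from the plan. Only the loss of 0.1 to 0.2 percentage points is supported here, not the absolute level.
- The calculation assumes one test per look. The plan compares both one- and two-year survival, so about 9% is not an upper bound for the primary endpoint.

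**Conclusion.** The concern holds. Under the plan's own rule, survival is tested at two-sided 0.05 at the interim and again at the end, with nothing to control the pair. If a significant look is declared or acted on, the overall type I error is 8.7% at the patient fraction and 8.9% to 9.6% on the death scale, against a nominal 5%.

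The death-scale range rests on the assumed accrual, survival and final-analysis timing, and on one test per look, but every scenario examined lands near 9%. If the look is meant to have no inferential role, the error rate is 5%, but the plan must say so. This should be settled before any interim data are examined.

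**What to change.** Add one paragraph to Data and Statistics that adopts one of these:

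1. **Fixed split (Haybittle-Peto).** The interim difference is called significant only at two-sided p<0.001, and the final test uses 0.049. This holds 5% at any fraction of deaths and needs no further calculation.
2. **O'Brien-Fleming-type Lan-DeMets spending.** Levels are computed from the actual fraction of deaths at the look, and the plan first defines which deaths count. The interim level would be about 0.00001 at t = 0.20 and 0.0003 at t = 0.30, with a final level between 0.0498 and 0.0500.
3. **No inferential role.** The look will support no efficacy claim, and the final test stays at 0.05.

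Under 1 or 2, also state what follows if the boundary is crossed and who decides. In every case, report the number of deaths at the look.

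The cost is wording only; the timing of the look need not change. Option 1 takes final power from 80% to 79.8% (79.9% if the exact final level of 0.0496 at t = 0.364 is used), option 2 takes less over these fractions, and option 3 takes none. The real price of 1 and 2 is that an early claim becomes hard to make; under option 2, at the death fractions expected here, it would be close to impossible. Options 1 and 3 are therefore the practical choices.
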